### ***6.2.4 Dermatology Life Quality Index***

The Dermatology Life Quality Index (DLQI) is a simple, patient-administered, 10-question, validated, quality-of-life questionnaire that covers 6 domains including symptoms and feelings,

daily activities, leisure, work and school, personal relationships, and treatment. The recall period of this scale is over the “last week.” Response categories include “not at all,” “a little,” “a lot,” and “very much,” with corresponding scores of 0, 1, 2, and 3 respectively and unanswered or “not relevant” responses scored as 0. For question 7 the response category ‘yes’ is scored 3, while a ‘no’ response is scored as 2, 1, or 0 based on the follow-up question response “a lot”, “a little”, or “not at all” respectively. The DLQI total score will be obtained by summing the scores from the 10 questions with a minimum score of 0 and a maximum score of 30. If any one of the 10 questions is unanswered, that question is scored as 0. However, if 2 or more questions are not answered then the DLQI score will not be calculated.

The DLQI will be assessed at baseline and at Weeks 1, 4, 8, 12, and 16 post-randomization, plus at the early termination visit, if applicable. At each of the post-baseline visits the DLQI total score will be computed along with the change from baseline. Descriptive statistics for the value, change from baseline will be tabulated for each time point.

The MMRM and ANCOVA analyses described in [Section 6.2.1](#) will be performed to compare the baricitinib treatment arms and placebo for change from baseline in the DLQI total score.

A DLQI responder is defined as a patient with a 4-point or greater decrease from baseline in the DLQI total score. At each post-baseline time point and the last observation the number and percent of DLQI responders will be compared between each baricitinib arm and placebo using a two-sided Fisher’s Exact test at level  $\alpha = 0.05$ . This analysis will be performed using only patients with a baseline DLQI total score greater than or equal to 4 points.

Individual domain DLQI scores may be analyzed in post-hoc analyses.

### **6.2.5 Itch Numerical Rating Scale**

The Itch Numerical Rating Scale (NRS): The Itch NRS is a patient-administered, 11 point horizontal scale anchored at 0 and 10, with 0 representing “no itch” and 10 representing “worst itch imaginable.” The patient indicates the overall severity of itching that best describes the worst level of itching in the past 24 hours.

The Itch NRS will be assessed at baseline and at Weeks 1, 4, 8, 12, and 16 post-randomization, plus at the early termination visit, if applicable. At each of the post-baseline visits the Itch NRS score will be computed along with the change and percent change from baseline. Descriptive statistics for the value and changes from baseline will be tabulated for each time point.

The number and percent of patients with an Itch NRS score of 0 “no itch” will be compared between the baricitinib arms and the placebo arm at each time point including baseline using an NRI analysis. Patients who either discontinue study treatment or discontinue from the study for any reason will be defined as non-responders for the NRI analysis for all assessments that were not collected. Randomized patients without at least 1 post-baseline observation of Itch NRS will also be defined as non-responders for the NRI analysis. The proportion of patients with no itch in the placebo arm will be compared to the proportion of patients in each of the baricitinib arms (2 mg and 4 mg) using two-sided Fisher’s exact tests with  $\alpha=0.05$ . The number and percentage of patients with no itch will be presented for each treatment arm at each time point including the patient’s last assessment. The p-values for the pairwise Fisher’s Exact tests will also be tabulated.

In addition, a bar chart that shows the percent of patients with no itch for each treatment arm at each time point including the patient's last assessment will be presented. The figure display will be generated for the overall population and by country.

The MMRM and ANCOVA analyses described in [Section 6.2.1](#) will be performed to compare the baricitinib treatment arms and placebo for change from baseline in the Itch NRS scores. The tabular outputs for the MMRM and ANCOVA analyses described will be provided.

## 6.3 Exploratory Efficacy Analyses

### 6.3.1 Patient-Oriented Eczema Measure

The Patient Oriented Eczema Measure (POEM) is seven-item patient-administered tool that focuses on the atopic dermatitis experienced by the patient. This tool has a one week recall period. Each question is scored on a five point scale (0 = no days; 1 = 1-2 days; 2 = 3-4 days; 3 = 5-6 days; 4 = every day), with a total score ranging from 0 to 28. If a single question is left unanswered, then that question is scored as 0. If more than one question is unanswered, then the tool is not scored.

The POEM score will be calculated at baseline and at Weeks 1, 4, 8, 12, and 16 post-randomization, plus at the early termination visit, if applicable. At each of the post-baseline visits the POEM score will be compared with the POEM score obtained at baseline to obtain change and percent change from baseline. Descriptive statistics for the value, change and percent change from baseline will be tabulated for each time point.

The MMRM and ANCOVA analyses described in [Section 6.2.1](#) will be performed to compare the baricitinib treatment arms and placebo for change from baseline in the POEM score. The tabular outputs for the MMRM and ANCOVA analyses described therein will be provided.

The POEM score can be banded as follows:

- 0 to 2 = Clear or almost clear
- 3 to 7 = Mild eczema
- 8 to 16 = Moderate eczema
- 17 to 24 = Severe eczema
- 25 to 28 = Very severe eczema

At each time point, baseline and post-baseline, the banded POEM score will be compared between each baricitinib arm and placebo using chi-square statistics with the row mean scores option. The number and percentage of patients in each band on the scale will be tabulated for each treatment arm and each time point. The associated p-values at each time point will be presented for each pairwise comparison. A bar chart that shows the distribution of patients among the bands for each treatment arm at each time point including the patient's last assessment will be presented.

Exploratory analyses may examine individual POEM items.

### **6.3.2 Analyses for Actigraphy Device data**

Hypoallergenic wrist watch-like devices will be worn by the patients throughout the study. A total of three devices will be worn – one device captures activity and sleep while two high-resolution devices, one worn on each arm, determine nocturnal scratching. Data from the devices will be used to summarize sleep/wake patterns and quantify nocturnal scratching events.

Data from the actigraphy devices will be downloaded at Weeks 1, 4, 8, 12, and 16 post-randomization, plus at the early termination visit, if applicable. Reproducibility of the data from day-to-day is fairly high, so results from the seven days prior to each download will be averaged to derive the response variables. Data from baseline will be available as part of the Week 1 download. At each of the post-baseline visits change from baseline will be computed for each of the response variables.

Additional exploratory analyses may be done, for example evaluating area under the curve to compare treatment groups.

#### **6.3.2.1 Analyses for Sleep/Wake Patterns**

At each time point the following parameters will be analyzed: average number of sleep disturbances per night-hour, duration of sleep, time of initial disturbance after sleep onset (WASO), onset latency, wake time, percent of time awake, number of wake bouts, fragmentation and sleep efficiency. The MMRM analysis described in [Section 6.2.1](#) will be performed to compare the baricitinib treatment arms and placebo for change from baseline for each of the variables. The tabular outputs for the MMRM analyses will be provided.

#### **6.3.2.2 Analyses for Nocturnal Scratching**

Three variables will be computed to assess nocturnal scratching – the average number of scratching events per night, the average time spent actively scratching during the night, and the average number of scratching events per hour. The MMRM analysis described in [Section 6.2.1](#) will be performed to compare the baricitinib treatment arms and placebo for change from baseline for each of the nocturnal itching variables. The tabular outputs for the MMRM analyses will be provided.

### **6.3.3 Analyses for Quick Inventory of Depressive Symptomatology – Self Report 16**

The Quick Inventory Depressive Symptomatology - Self Report 16 (QIDS-SR16) is a self-administered 16-item instrument intended to assess the existence and severity of symptoms of depression. The QIDS-SR16 scale is used to assess the potential impact of treatment on new onset or changes in depression, thoughts of death, and /or suicidal ideation severity. A patient is asked to consider each statement as it relates to the way they have felt for the past 7 days. There is a 4-point scale for each item ranging from 0 to 3. The 16 items corresponding to 9 depression domains are summed to give a single score ranging from 0 to 27, with higher scores denoting greater symptom severity. The domains assessed by the instrument include: (1) sad mood, (2) concentration, (3) self-criticism, (4) suicidal ideation, (5) interest, (6) energy/fatigue, (7) sleep disturbance (initial, middle, and late insomnia or hypersomnia), (8) decrease/increase in appetite/weight, and (9) psychomotor agitation/retardation. The score is derived by adding the

following nine numbers – results from questions 5 (depressed mood), 10 (concentration), 11 (worthlessness/guilt), 12 (suicidal ideation), 13 (decreased interest), 14 (decreased energy) plus the highest scores from questions 1-4 (sleep), 6-9 (weight/appetite changes), and 15-16 (psychomotor changes), respectively. If any single question is left unanswered, then that question is scored as 0.

The QIDS-SR16 will be assessed at baseline and at Weeks 1, 4, 8, 12, and 16 post-randomization, plus at the early termination visit, if applicable. At each of the post-baseline visits the QIDS-SR16 domain scores and total score will be calculated, and the scores will be compared with the respective baseline score to obtain change and percent from baseline. Descriptive statistics for the value and changes from baseline will be tabulated for each domain and total score and at each time point.

The QIDS-SR16 total score will be categorized as follows:

- 0 to 5 = No depression
- 6 to 10 = Mild depression
- 11 to 15 = Moderate depression
- 16 to 20 = Severe depression
- 21 to 27 = Very severe depression

At each time point, baseline and post-baseline, the level of depression will be compared between each baricitinib arm and placebo using chi-square statistics with the row mean scores option. The number and percentage of patients in each depression level will be tabulated for each treatment arm and each time point. The associated p-values at each time point will be presented for each pairwise comparison. A bar chart that shows the distribution of patients among the bands for each treatment arm at each time point including the patient's last assessment will be presented. The table and figure displays will be generated for the overall population and for patients enrolled in Japan.

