## 2.8 Reporting Conventions

This section details the general conventions to be used for the statistical analyses. Departures from these general conventions will be provided in the specific detailed sections of this analysis plan. The following conventions will be applied to all data presentations and analyses:

- Data will be summarized for the following groups:
  - Overall, Placebo, 2mg LY, 4mg LY will be used for patient accounting and disposition
  - Placebo, 2mg LY, and 4mg LY for all presentations except patient accounting and disposition
- Continuous variables will generally be summarized by the number of patients, mean, standard deviation, median, minimum, and maximum. Exceptions to these conventions will be specifically noted. Categorical variables will be summarized by the number and percentage of patients within each category.
- All mean and median values will be formatted to one more decimal place than the measured value.
- Standard deviation values will be formatted to two more decimal places than the measured value.
- Minimum and maximum values will be presented with the same number of decimal places as the measured value.
- The number and percent of responses will be presented in the form XX (XX %), where the percentage is in parentheses. Percentages will be rounded to the nearest percent. In the case of a frequency of zero, the frequency and percentage will be presented as 0 rather than 0 (0%).

- All summary tables will include the analysis population sample size (i.e., number of patients) in each treatment group.
- Date variables will be formatted as ddMMYY for presentation.

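### SAP Section 6.3.3 names new onset of depression and suicidal ideation as a purpose of the QIDS-SR16, but no planned output counts it

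*SAP*

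**What the plan says.** SAP Section 6.3.3 gives the reason for collecting the QIDS-SR16: it "is used to assess the potential impact of treatment on new onset or changes in depression, thoughts of death, and /or suicidal ideation severity". The section then plans three kinds of output.

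- Summaries of scores: "Descriptive statistics for the value and changes from baseline will be tabulated for each domain and total score and at each time point". Suicidal ideation (question 12) is one of the nine domains, so it has its own rows. Section 2.8 fixes the content: "Continuous variables will generally be summarized by the number of patients, mean, standard deviation, median, minimum, and maximum".
- A table of the five depression bands: "The number and percentage of patients in each depression level will be tabulated for each treatment arm and each time point". With it comes the section's only between-arm test: "the level of depression will be compared between each baricitinib arm and placebo using chi-square statistics with the row mean scores option", done separately at baseline and at each later visit.
- A bar chart of the same bands by arm and time point, including the last assessment.

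The bands are cut from the total score. Sleep enters that total as one domain: six single questions are added, "plus the highest scores from questions 1-4 (sleep), 6-9 (weight/appetite changes), and 15-16 (psychomotor changes), respectively".

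Section 6.3.3 does not cross-tabulate a patient's baseline band with a later band, count patients whose question 12 score rises from 0, or use a worst post-baseline value. The SAP plans shift tables in Section 7.3.2, for laboratory parameters only.

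**The concern.** A new-onset case is a patient without the condition at baseline who has it later. Counting such cases needs the baseline and the later value of the same patient, set against a threshold. The band table gives the margins at each visit, so patients who enter a band and patients who leave it cancel. The change summaries do use each patient's own baseline, but they report group statistics and not numbers of patients.

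What is at stake is one stated purpose of the scale, and it is a safety question. With the plan followed exactly, the report could not state for any arm how many patients became newly depressed, or how many newly reported suicidal ideation on this scale, although the data to do so are collected at baseline and at five post-baseline visits.

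**Working it through.** **The plan's own figure.** The item scale is stated as "There is a 4-point scale for each item ranging from 0 to 3", and the total as "The 16 items corresponding to 9 depression domains are summed to give a single score ranging from 0 to 27". Nine domains with a maximum of 3 each give 9 × 3 = 27, so the range reproduces. The bands 0–5, 6–10, 11–15, 16–20 and 21–27 cover it without gap or overlap. The scoring is not in question.

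**Arm sizes.** SAP Section 1.3 gives about 120 patients at 4:3:3, so 120 × 4/10 = 48 on placebo and 120 × 3/10 = 36 on each baricitinib dose.

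**What the band table can say about new onset.** Let n be the patients assessed at both visits, b those depressed (any band above the lowest) at baseline, and w those depressed at the later visit. At most b of the w were already depressed, so at least w − b are new. New cases cannot exceed w, nor the n − b patients who were free of depression at baseline. Hence

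max(0, w − b) ≤ new cases ≤ min(w, n − b).

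The SAP gives no expected rates, so b and w below are assumed.

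| n | b | w | Lower bound | Upper bound |
|---|---|---|---|---|
| 36 | 4 | 4 | max(0, 0) = 0 | min(4, 32) = 4 |
| 36 | 7 | 7 | max(0, 0) = 0 | min(7, 29) = 7 |
| 36 | 11 | 7 | max(0, −4) = 0 | min(7, 25) = 7 |
| 48 | 10 | 10 | max(0, 0) = 0 | min(10, 38) = 10 |

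In each row the planned table fits both no new case and every later case being new. The row mean scores test uses the same margins and cannot narrow the range.

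**What the change summaries can say.** Suppose that in an arm of 36 the ideation score rises by 2 in three patients and falls by 1 in six. The mean change is (3 × 2 − 6 × 1)/36 = 0, but the maximum change is +2, so the table does reveal that someone worsened. It would also read +2 if only one patient had risen by that much. The standard deviation reflects the number and the size of the changes together and does not yield a count. Nor does a change separate onset from worsening: 0 to 1 and 1 to 2 are both a change of +1.

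**Across visits.** Each visit is tabulated alone. A patient with ideation only at Week 4 and another with it only at Week 12 appear in different rows, and the number of patients ever affected cannot be recovered from them.

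**Where sleep enters.** Sleep contributes 0 to 3 of the 27 points. If ideation goes from 0 to 3 and sleep from 3 to 0, the total changes by 3 − 3 = 0 and the band stays the same. The separate ideation rows would still show a maximum change of +3.

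**The case against.** The plan covers much of the purpose. Section 6.3.3 speaks of new onset or changes, and change is summarised for every domain. The arms are randomised, so a net shift in depression level caused by treatment can appear in the comparison at each visit. The scale stands under exploratory efficacy and is not among the endpoints in Table JAHG.1. Depression or ideation reported as an adverse event is counted by preferred term under Section 7.2.1, and serious events are listed under Section 7.2.3. Section 1.1 allows further exploratory analyses without an SAP amendment.

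All of this stands, and it lowers the weight of the point. It does not supply the count. Adverse-event reporting does not replace a count from a questionnaire given at every visit, and an analysis that may be added later is not a planned one.

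A reader might infer two stronger things. The first is that nothing in the plan links a patient to his or her own baseline. That is not so: change from baseline is a within-patient quantity and is tabulated for the total and all nine domains. The second is that better sleep, which is plausible in a trial that also studies itch and sleep, could hide emerging ideation in every output. It could offset ideation in the total and the bands, but not in the ideation domain, which is reported on its own with minimum and maximum. Nor is a total without sleep needed: for the same patients, its mean change is the mean total change minus the mean sleep-domain change, and both are already planned.

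**Conclusion.** The point holds in a limited form. New onset of depression and of suicidal ideation is a stated purpose of the scale, and no planned output counts it. The score summaries can show that at least one patient worsened, but not how many or from what level. The band table and the only between-arm test are cross-sectional and rest on a total that includes sleep.

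The size is modest. No sample size, power or error rate is affected, and the change part of the purpose is covered descriptively. The bounds follow from the margins alone, and the band counts used to illustrate them are assumptions. Treating any band above the lowest as depressed is also a convention chosen for the illustration: a move from 5 to 6 points crosses it, so a new case in that sense need not be a clinical diagnosis.

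**What to change.** Add to Section 6.3.3, by treatment arm and from baseline to worst post-baseline value:

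1. A shift table of the five depression bands, baseline band by worst later band.
2. The number and percentage of patients with question 12 equal to 0 at baseline and 1 or more at any post-baseline visit, and the number and percentage with any increase in question 12 from baseline.

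Keep the planned tables, test and bar chart. State the denominators, and add a footnote that a single unanswered question is scored 0 under the existing rule, because a skipped question 12 would otherwise read as no ideation.

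The cost is the programming and checking of two small descriptive tables. No new data, visits or tests are needed.

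### QIDS-SR16: a skipped suicidal ideation question is scored as no ideation, and no rule withholds the score when two or more questions are unanswered

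*SAP*

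**What the plan says.** SAP Section 6.3.3 gives the scale's purpose as assessing the effect of treatment on depression, "thoughts of death, and /or suicidal ideation severity". On items it says: "There is a 4-point scale for each item ranging from 0 to 3". The items are "summed to give a single score ranging from 0 to 27, with higher scores denoting greater symptom severity".

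The total adds nine domain scores. Six domains are one question each (5, 10, 11, 12, 13, 14), and question 12 is suicidal ideation. The other three take the highest score among questions 1-4, 6-9 and 15-16.

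The only missing-item rule is: "If any single question is left unanswered, then that question is scored as 0". Nothing follows it about two or more unanswered questions, and question 12 is not excepted.

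Values and changes from baseline are tabulated for every domain and the total at each time point. The total is also cut into five bands (0-5, 6-10, 11-15, 16-20, 21-27). These are compared between each baricitinib arm and placebo by a row-mean-scores test and charted, including at the last assessment.

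Two other questionnaires also score one unanswered question as 0, but add a limit. Section 6.2.4 (DLQI): "However, if 2 or more questions are not answered then the DLQI score will not be calculated". Section 6.3.1 (POEM): "If more than one question is unanswered, then the tool is not scored". Section 2.3 deals with missing assessments and dates, not missing items, so it does not override the QIDS-SR16 rule.

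**The concern.** The rule turns the absence of an answer into the most favourable answer. Where a domain has several questions, the others can still carry the score. Where it has one, nothing can. For question 12 the result is a recorded absence of suicidal ideation that the patient never reported.

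This goes directly into the ideation row of the domain table and, through the total, into the band that is tested. No other rating of depression or suicidality is planned in Section 7, and neither is among the adverse events of special interest in Section 7.2.7. The QIDS-SR16 tables are therefore where a reader would look for ideation severity.

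**Working it through.** **Reproducing the stated range.** Nine domains, each 0 to 3: 9 × 3 = 27. This matches the 0 to 27 in Section 6.3.3.

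**What one skipped question does to a visit total.**
- Single-question domain (5, 10-14): the loss equals the hidden answer, 0 to 3. With every item at 3, skipping question 12 gives 27 − 3 = 24.
- Multi-question domain: there is a loss only if the skipped question was the sole highest. With every item at 3, skipping question 1 leaves 27.
- The total can never rise.

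**Effect on the depression band when question 12 is skipped.** Let R be the sum of the other eight domains, so R runs from 0 to 8 × 3 = 24, which is 25 values. If the hidden answer is k, the true total is R + k and the recorded total is R. The band drops when a boundary lies between them.

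| Hidden answer k | True totals at which the band drops | Count |
|---|---|---|
| 1 | 6, 11, 16, 21 | 4 of 25 |
| 2 | 6, 7, 11, 12, 16, 17, 21, 22 | 8 of 25 |
| 3 | 6, 7, 8, 11, 12, 13, 16, 17, 18, 21, 22, 23 | 12 of 25 |

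For example, a true total of 8 (mild) with k = 3 is recorded as 5 (no depression). The drop is never more than one band, because each band spans at least five totals. These are counts of possible totals, not probabilities: the SAP gives no distribution of scores.

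**Effect on change from baseline.** Take a patient whose true ideation score is 2 at both visits, so the true change is 0.
- Question skipped after baseline: recorded change 0 − 2 = −2, a false improvement.
- Question skipped at baseline: recorded change 2 − 0 = +2, a false new onset.

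**Two or more unanswered questions.** The rule can be read in two ways.
- If it applies to each unanswered question, two skipped single-question domains hide up to 2 × 3 = 6 points, all six hide up to 6 × 3 = 18, and a blank form scores 0, in the no-depression band.
- If it applies to exactly one unanswered question, the SAP has no rule for two or more, and the programmer must invent one.

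Under either reading, the limit given for the DLQI and POEM is absent.

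**The case against.** Scoring one unanswered item as 0 is this SAP's common convention, since the DLQI and POEM do the same. That is correct, so those scales support only the limit on the number of missing items. The case for question 12 rests on other grounds: it is a whole domain by itself, that domain is tabulated separately, and the SAP names ideation as a purpose of the scale.

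The scale is listed under exploratory efficacy and does not appear in the objectives table (Table JAHG.1). The ideation domain is only described, not tested. Adverse events are reported independently, and eCRF data are supplied in SDTM datasets, so a derived 0 need not erase the original record. All of this stands and limits the weight of the point.

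A reader might infer that the SAP imputes without limit. The text does not establish this. In the POEM section the comparable wording about a single question means exactly one, because the next sentence treats more than one separately. The 6-point, 18-point and blank-form results therefore hold under one reading only.

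A reader might also infer that the rule hides a safety signal or favours baricitinib. The documents do not show that. The trial is double-blind, nothing indicates that skipping would differ by arm, no rate of skipped items is given, and the error in change scores can go in either direction.

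**Conclusion.** The point holds. Followed as written, the plan records a skipped question 12 as no suicidal ideation, and this needs only one unanswered question, so it does not depend on how the rule is read. The visit total is understated by up to 3 of 27 points, with a one-band drop at 4, 8 or 12 of 25 possible totals for a hidden answer of 1, 2 or 3. There is no error in the score if the true answer was 0. Change from baseline may be too low or too high.

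Separately, the treatment of two or more unanswered questions is either unlimited zero scoring or undefined, and the wording does not settle which.

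The consequence is confined to the exploratory depression and ideation summaries and the band comparison. How many patients would be affected cannot be estimated from the SAP. The change is worth making because it is specific and cheap.

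**What to change.** Amend Section 6.3.3 as follows:

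1. If question 12 is unanswered, do not score it as 0. Set the ideation domain to missing, and report the number missing by arm and visit, including baseline.
2. Set any other single-question domain to missing when its question is unanswered. In the three multi-question domains, use the highest answered question.
3. Do not calculate the total or the band when question 12 is unanswered, or when two or more questions are unanswered, in line with the DLQI and POEM limits.
4. State how the total is formed when exactly one question other than 12 is unanswered. Counting it as 0 in the total keeps the convention used for the DLQI and POEM. Prorating is not proposed: the SAP offers no basis for a threshold, and prorating over a missing question 12 would impute it from the other eight domains.
5. Define which questions count towards the limit. The appetite and weight domain covers both decrease and increase, and the SAP does not say whether every patient is meant to answer all of questions 6-9. Check the form, so that questions left blank by design are not counted as unanswered.

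The cost is SAP wording, a small programming change, and a few exploratory totals and bands becoming missing. The change should be made before the unblinded review described in Section 2.1.

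### Percent change is planned for QIDS-SR16 domain and total scores that can be 0 at baseline, where it is undefined and leaves out the patients in whom new onset would show

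*SAP*

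**What the plan says.** SAP Section 6.3.3 describes the items thus: "There is a 4-point scale for each item ranging from 0 to 3". Nine domain scores are formed: six single items, "plus the highest scores from questions 1-4 (sleep), 6-9 (weight/appetite changes), and 15-16 (psychomotor changes), respectively". They are "summed to give a single score ranging from 0 to 27, with higher scores denoting greater symptom severity", so 0 is the best score for each domain and for the total. A single unanswered question is scored 0.

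On derivation, the section says that "the scores will be compared with the respective baseline score to obtain change and percent from baseline". This covers both kinds of score: "At each of the post-baseline visits the QIDS-SR16 domain scores and total score will be calculated". In the first of these two quotes the word change is missing after percent, but percent change is the natural reading, because Section 6.2.5 uses the parallel wording in full for the Itch NRS. On output: "Descriptive statistics for the value and changes from baseline will be tabulated for each domain and total score and at each time point".

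The section says the scale is there to "assess the potential impact of treatment on new onset or changes in depression, thoughts of death, and /or suicidal ideation severity".

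The only QIDS-SR16 comparison with p-values is on the banded total score (no depression to very severe), each baricitinib arm against placebo. The SAP has no rule for percent change when the baseline is 0.

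**The concern.** Percent change divides by the baseline score. On a 0 to 3 domain the value 0 means that the symptom is absent, and a patient who starts there has no percent change whatever happens later. New onset in a domain is a move from 0 to a positive score, so the percent statistic leaves out the event that the section wants to see. This part needs no assumption about the data.

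The patients who remain start at 1, 2 or 3. Those at 0, who can only stay or worsen, have been removed, so ordinary fluctuation among the rest no longer balances out. The statistic is also asymmetric: 1 to 2 is +100%, while 2 to 1 is -50%. The two effects pull in opposite directions, and which one wins depends on how many patients score 0.

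At stake is the readability of one descriptive display. It is, however, the only planned QIDS-SR16 output at domain level, and so the only one that shows suicidal ideation separately. A shift in one domain need not move a patient's total-score band.

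**Working it through.** **Range.** Six single items plus three highest-of groups give nine domain scores of 0 to 3: 9 × 3 = 27. This reproduces the stated total range of 0 to 27. It also confirms that every domain, and the total, can be 0.

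**Patients without a percent change.** (Y - 0)/0 has no value. Section 1.3 gives about 120 patients allocated 4:3:3, that is 48/36/36. If a share p0 score 0 at baseline in a domain, the number lost is p0 × n:

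| p0 (assumed) | placebo | 2 mg | 4 mg |
|---|---|---|---|
| 0.25 | 12 | 9 | 9 |
| 0.50 | 24 | 18 | 18 |
| 0.80 | 38 | 29 | 29 |

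**Mean percent change when the group does not move.** Let baseline X and follow-up Y have the same distribution on 0 to 3. The SAP gives no such distribution, so those below are assumptions. In Model A, Y keeps the value X with probability r and is otherwise redrawn independently. The mean over patients with X > 0 is then

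(1 - r) × {E[Y] × E[1/X | X > 0] - 1}.

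For 60/25/10/5% at 0/1/2/3:
- E[Y] = 0.25 + 2 × 0.10 + 3 × 0.05 = 0.60.
- E[1/X | X > 0] = (0.25 + 0.10/2 + 0.05/3)/0.40 = 0.3167/0.40 = 0.792.
- 0.60 × 0.792 = 0.475, so the mean is -52.5% at r = 0, -26.2% at r = 0.5 and -15.8% at r = 0.7.
- At r = 1 (no patient changes) it is exactly 0%.

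Model B lets scores move only one point at a time (proposal probability 0.4, reversible, so the group distribution is again unchanged). It gives -19.2%.

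**Dependence on the share at 0.**

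| Assumed % at 0/1/2/3 | Model A, r = 0.5 | Model B |
|---|---|---|
| 90/7/2/1 | -44% | -23% |
| 60/25/10/5 | -26% | -19% |
| 40/30/20/10 | -14% | -12% |
| 25/25/25/25 | -4% | -4% |
| 20/30/30/20 | -2% | -1% |
| 10/30/35/25 | +4% | +4% |
| 5/25/40/30 | +6% | +5% |
| 0/33/33/33 | +11% | +9% |

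In these examples the sign turns when roughly 10 to 20% score 0.

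**Worsenings left out.** For 60/25/10/5% with independent redraws, worsenings from 0, 1 and 2 have probability 0.60 × 0.40 = 0.24, 0.25 × 0.15 = 0.0375 and 0.10 × 0.05 = 0.005, total 0.2825. The share from 0 is 0.24/0.2825 = 85%.

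**Absolute change on the same data.** For 60/25/10/5% and r = 0, patients above 0 change by 0.60 - 1.50 = -0.90 on average and those at 0 by +0.60. Together: 0.40 × (-0.90) + 0.60 × 0.60 = 0. Absolute change, which is already planned, gives the correct answer with every patient kept.

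**The case against.** The case for leaving the text alone is that little depends on it. The section is exploratory and percent change is only described. Value and absolute change stand in the same table and keep every assessed patient who moves up from 0. The p-values use total-score bands, and those displays would show a patient leaving the no-depression band. Section 2.8 reports the number of patients with each continuous summary, so a shrinking denominator would be visible. All of this stands, and it is why the point is minor.

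A reader might go further than the SAP allows in four ways:
- **That percent change shows improvement when nothing has changed.** If no patient changes, it is 0%. The spurious mean needs individual fluctuation and many zeros, and with few zeros it points the other way.
- **That 0 is the usual baseline in most domains.** The SAP gives no distribution. The no-depression band is a cut-off, not a description of these patients, and the sleep domain, as the highest of four items, may have few zeros.
- **That the table drops patients who go from 0 to a positive score.** Only the percent-change columns do.
- **That the output therefore gives false reassurance in every arm.** The absolute-change columns beside it prevent that conclusion.

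What the objection does not remove is that the statistic is undefined at a baseline of 0, that no rule covers this, and that it omits the very patients needed to see new onset.

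**Conclusion.** Wrong as written, low severity. It follows from the SAP's own scoring that percent change is undefined at a baseline of 0 for any QIDS-SR16 domain and for the total, and that the statistic excludes the patients in whom new onset would appear. The denominator will differ between domains, and unanswered questions scored 0 can add to the zeros.

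The size and direction of any misleading mean rest on assumed baseline distributions and on how much individual scores fluctuate. The clearest false improvement arises where zeros are common; where they are few, the error is a smaller false worsening. No hypothesis test and no primary or secondary result is affected.

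**What to change.** In Section 6.3.3, delete percent change for the QIDS-SR16 domain and total scores and keep value and absolute change. Optionally add, per domain, arm and visit, the number of patients who score 0 at baseline and a positive score at that visit, with the number at 0 at baseline as denominator. This would show new onset directly.

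Confine the change to QIDS-SR16. A general rule against percent change for scores that can be 0 would, read literally, reach the planned percent change in EASI, SCORAD, Itch NRS and POEM. Percent change in EASI is part of a secondary objective.

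The cost is one wording edit and fewer table columns. No information is lost, because value and absolute change remain. The optional count adds one line per domain.
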